11. MEASUREMENT OF EFFECT

Antitumor Effect

For the purposes of this study, patients should be re-evaluated for response every 12 weeks and earlier if clinically required. Response and progression will be evaluated in this study using the new international criteria proposed by the Response Evaluation Criteria in Solid Tumors (RECIST 1.1)[26]. Changes in only the largest diameter (unidimensional measurement) of the tumor lesions are used in the RECIST criteria.

All patients will be evaluable for toxicity from the time of their first treatment with Carfilzomib. Only those patients who have measurable disease present at baseline, have received at least one cycle of therapy, and have had their disease re-evaluated will be considered evaluable for response. These patients will have their response classified according to the definitions stated below. (Note: Patients who exhibit objective disease progression prior to the end of cycle 1 will also be considered evaluable.)

Measurable disease. Measurable lesions are defined as those that can be accurately measured in at least one dimension (longest diameter to be recorded) as ≥ 20 mm with conventional techniques (CT, MRI, x-ray) or as ≥ 10 mm with spiral CT scan. Lymph nodes are considered measurable if the short axis diameter is ≥ 15 mm. All tumor measurements must be recorded in millimeters (or decimal fractions of centimeters). Tumor lesions that are situated in a previously irradiated area might or might not be considered measurable

Non-measurable disease. All other lesions (or sites of disease), including small lesions (longest diameter < 20 mm with conventional techniques or < 10 mm using spiral CT scan), are considered non-measurable disease. Bone lesions, leptomeningeal disease, ascites, pleural/pericardial effusions, lymphangitis cutis/pulmonis, inflammatory breast disease, abdominal masses (not followed by CT or MRI), and cystic lesions are all non-measurable.

Bone disease: According to PCWG-2 guidelines, 2 distinct new lesions on bone scan consistent with bone metastases in the best judgment of the investigator and confirmed by further new lesions on a subsequent scan ≥ 6 weeks later is defined as bone scan progression.

Target lesions. All measurable lesions up to a maximum of 2 lesions per organ and 5 lesions in total, representative of all involved organs, should be identified as target lesions and recorded and measured at baseline. Target lesions should be selected on the basis of their size (lesions with the longest diameter) and their suitability for accurate repeated measurements (either by imaging techniques or clinically). A sum of the longest diameter (LD) for all target lesions will be calculated and reported as the baseline sum LD. The baseline sum LD will be used as reference by which to characterize the objective tumor response.

Non-target lesions. All other lesions (or sites of disease) including any measurable lesions over and above the 5 target lesions should be identified as non-target lesions and should also be recorded at baseline. Measurements of these lesions are not required, but the presence or absence of each should be noted throughout follow-up.

Methods for Evaluation of Measurable Disease

All measurements should be taken and recorded in metric notation using a ruler or calipers. All baseline evaluations should be performed as closely as possible to the beginning of treatment and never more than 4 weeks before the beginning of the treatment. The same method of assessment and the same technique should be used to characterize each identified and reported lesion at baseline and during follow-up. Imaging-based evaluation is preferred to evaluation by clinical examination when both methods have been used to assess the antitumor effect of a treatment.

Clinical lesions will only be considered measurable when they are superficial (e.g., skin nodules and palpable lymph nodes). In the case of skin lesions, documentation by color photography, including a ruler to estimate the size of the lesion, is recommended. Lesions on chest x-ray are acceptable as measurable lesions when they are clearly defined and surrounded by aerated lung. However, CT is preferable.

CT and MRI should be performed with cuts of 10 mm or less in slice thickness contiguously. Spiral CT should be performed using a 5 mm contiguous reconstruction algorithm. This applies to tumors of the chest, abdomen, and pelvis. Head and neck tumors and those of extremities usually require specific protocols.

Ultrasound (US) should not be used to measure tumor lesions. It is, however, a possible alternative to clinical measurements of superficial palpable lymph nodes, subcutaneous lesions, and thyroid nodules. US might also be useful to confirm the complete disappearance of superficial lesions usually assessed by clinical examination.

The utilization of endoscopy techniques for objective tumor evaluation has not yet been fully and widely validated. Their uses in this specific context require sophisticated

equipment and a high level of expertise that may only be available in some centers. Therefore, the utilization of such techniques for objective tumor response should be restricted to validation purposes in reference centers. However, such techniques may be useful to confirm complete pathological response when biopsies are obtained.

Tumor markers alone cannot be used to assess response. If markers are initially above the upper normal limit, they must normalize for a patient to be considered in complete clinical response. Specific additional criteria for standardized usage of prostate-specific antigen (PSA) and CA-125 response in support of clinical trials are being developed.

The cytological confirmation of the neoplastic origin of any effusion that appears or worsens during treatment when the measurable tumor has met criteria for response or stable disease is mandatory to differentiate between response or stable disease (an effusion may be a side effect of the treatment) and progressive disease.

Response Criteria for the evaluation of Target Lesions

Complete Response (CR): Disappearance of all target lesions

Partial Response (PR): At least a 30% decrease in the sum of the longest diameter (LD) of target lesions, taking as reference the baseline sum LD

Progressive Disease (PD): At least a 20% increase in the sum of the LD of target lesions, taking as reference the smallest sum LD recorded since the treatment started or the appearance of one or more new lesions

Stable Disease (SD): Neither sufficient shrinkage to qualify for PR nor sufficient increase to qualify for PD, taking as reference the smallest sum LD since the treatment started

Evaluation of Non-Target Lesions

Complete Response (CR): Disappearance of all non-target lesions and normalization of tumor marker level

Note: If tumor markers are initially above the upper normal limit, they must normalize for a patient to be considered in complete clinical response.

Incomplete Response/Stable Disease (SD): Persistence of one or more non-target lesion(s) and/or maintenance of tumor marker level above the normal limits

Progressive Disease (PD): Appearance of one or more new lesions and/or unequivocal progression of existing non-target lesions

Although a clear progression of “non-target” lesions only is exceptional, the opinion of the treating physician should prevail in such circumstances, and the progression status should be confirmed at a later time by the review panel (or Principal Investigator).

Evaluation of Best Overall Response

The best overall response is the best response recorded from the start of the treatment until disease progression/recurrence (taking as reference for progressive disease the smallest measurements recorded since the treatment started). The patient's best response assignment will depend on the achievement of both measurement and confirmation criteria.

Target Lesions	Non-Target Lesions	New Lesions	Overall Response	Best Response for this Category Also Requires:
CR	CR	No	CR	≥4 wks. confirmation
CR	Non-CR/Non-PD	No	PR	≥4 wks. confirmation
PR	Non-PD	No	PR	
SD	Non-PD	No	SD	documented at least once ≥4 wks. from baseline
PD	Any	Yes or No	PD	no prior SD, PR or CR
Any	PD*	Yes or No	PD	
Any	Any	Yes	PD	

* In exceptional circumstances, unequivocal progression in non-target lesions may be accepted as disease progression.
 
Note: Patients with a global deterioration of health status requiring discontinuation of treatment without objective evidence of disease progression at that time should be reported as “symptomatic deterioration”. Every effort should be made to document the objective progression even after discontinuation of treatment.
				

Duration of Response

The duration of overall response is measured from the time measurement criteria are met for CR or PR (whichever is first recorded) until the first date that recurrent or progressive disease is objectively documented (taking as reference for progressive disease the smallest measurements recorded since the treatment started).

The duration of overall CR is measured from the time measurement criteria are first met for CR until the first date that recurrent disease is objectively documented.

Duration of stable disease: Stable disease is measured from the start of the treatment until the criteria for progression are met, taking as reference the smallest measurements recorded since the treatment started.

Pain response and progression

Patients with a PPI score of at least 2, or need for analgesics, or both at baseline are assessed for the pain response. A pain response is defined as a two-point reduction in the PPI score from baseline without an increase in the analgesic use or as a reduction in analgesic use without an increase in the PPI score. Pain progression is defined as an increase in the PPI score of at least one point from the nadir, an increase in analgesic use, or a requirement for palliative radiotherapy.

Progression-Free Survival

PFS is defined as the duration of time from start of treatment to time of progression or death, whichever comes first.

12. **CORRELATIVE STUDIES**

Circulating Tumor Cell (CTC) enumeration will be used as a secondary marker for efficacy of response to the treatment. Baseline CTC will be obtained prior to initiation of therapy and day 1 of cycles 2 and 4. Baseline whole blood 20S proteasome activity will also be determined.

CTC enumeration

The CELLSEARCH[®] System led to the first standardized, FDA-cleared semi-automated system that detects and enumerates CTCs of epithelial origin (CD45-, EpCAM+, and cytokeratins 8, 18+, and/or 19+) from a 7.5-mL blood sample with high sensitivity and specificity. The CELLSEARCH[®] System uses unique immunomagnetic and fluorescence imaging technology to provide rapid and reproducible analysis of CTCs with a simple 3-step process: sample collection, sample preparation, and sample analysis. System components include:

- Proprietary CellSave Preservative sample tubes
- CELLSEARCH[®] CTC Test and Control kits
- Automated CELLTRACKS[®] AUTOPREP[®] System
- CELLTRACKS ANALYZER II[®]

CellSave Preservative tubes provide an optimized cell preservative that stabilizes CTCs for up to 96 hours at room temperature, which allows shipment of samples to remote locations for analysis and improves the reproducibility and reliability of CTC analysis. CTCs are fragile and tend to degrade within a few hours when collected in standard evacuated blood collection tubes.

Once the blood sample is collected for UAB patients, the tube will be delivered to UAB main laboratory to be sent out to Quest Diagnostics for CTC enumeration. For outside sites, the tube will be sent directly to Quest Diagnostics for CTC enumeration.

Whole Blood 20S Proteasome Activity

This analysis will be conducted at the UAB PK/PD Shared Facility directed by [name]. Blood should be stored at -70C or lower until shipment. The sample is shipped on dry ice to the UAB PK/PD Shared Facility. Ship the samples to Attention: [name]; University of Alabama at Birmingham School of Medicine; [name]. A 1.0 mL whole blood sample should be collected in a green-top (heparin) tube. The tube should be gently inverted several times, and then placed directly into the freezer at -70 or 80°. Samples can be batched and stored at -70 or 80°C, then shipped on dry ice. Ten (10) µL of whole blood will be added to 300µL of cold lysis buffer (5 mmol/L EDTA), mixed, and incubated on ice for 15 to 20 minutes. Samples will be centrifuged at 6,600 x g, 4°C, for 20 minutes. The resulting supernatant (200 µL) will be added to 200 µL of buffer [40 mmol/L HEPES (pH 8.0), 1 mmol/L EDTA, and 20% glycerol], mixed, and assayed

immediately or stored at -80°C. For 20S β 5 proteasome assay, lysates prepared from whole blood will be thawed at room temperature and diluted 1:5 with proteasome assay buffer [20 mmol/L HEPES, 0.5 mmol/L EDTA (pH 7.4)]. Five microliters of lysate will be added to wells of a 96-well plate followed by 100 μ L of proteasome assay buffer at 37°C containing 40 μ mol/L Suc-LLVY-AMC and 12 nmol/L recombinant human PA28 α . The progress curves will be monitored in a plate reader for 1 h at 37°C. The slopes of the progress curves will be converted to substrate turnover by use of an AMC calibration standard. 20S β 1 and β 2 proteasome assays can be done identically to the β 5 proteasome assay except the substrates Z-LLE-AMC and Z-VLR-AMC would be used respectively.

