2.2 Secondary Objectives

- PSA changes (response, PSA decline $\geq 30\%$ within 3 months)
- CTC changes (unfavorable \rightarrow favorable, $>30\%$ decline)
- Measurable disease response rate (RECIST)
- Pain responses (decline in present pain index ≥ 2 , decrease in analgesics)
- Overall Survival

- Toxicities
- Association of outcomes with baseline whole blood 20S proteasome level

[figure not shown]

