3. OVERALL TRIAL DESIGN

3.1 Design

This is a 2-center one-stage phase II trial conducted at UAB Comprehensive Cancer Center and outside sites, and managed by the CTNMO (Clinical Trial Network Monitoring Office) housed at the UAB Comprehensive Cancer Center. Clinical PFS as the primary end-point and the trial will enroll 28 patients. The eligible population includes men with metastatic CRPC who have received prior abiraterone and/or enzalutamide (prior chemotherapy and sipuleucel-T are allowed). Carfilzomib is administered twice-weekly on consecutive days (± 1 day) (days 1, 2, 8, 9, 15, 16) as a 30 minute intravenous (IV) infusion for 3 weeks every 4 weeks (1 cycle) with dexamethasone and acetaminophen premedication as well as normal saline 250 ml over 30 mins as pre-hydration. The dose of carfilzomib is 20 mg/m² on days 1 and 2 of cycle 1 and then escalated in succeeding weeks and cycles to 56 mg/m² for no dose limiting toxicities (DLTs) occur. DLTs are defined as any grade ≥ 3 non-hematologic toxicity or grade ≥ 4 neutropenia or thrombocytopenia lasting ≥ 7 days. Acyclovir 400 mg orally twice daily is required during therapy, which may be discontinued ≥ 7 days after the last dose of carfilzomib. Therapy will continue until progression (as defined below) or severe toxicities. Patients removed from the trial for toxicities or other reasons will continue to be followed until progression or starting a new agent. Androgen deprivation therapy with LHRH analogue or antagonist and bone protecting agent (denosumab or zoledronic acid) will also continue. Comprehensive metabolic panel (CMP) evaluations are performed on day 1 every 4 weeks, complete blood cell (CBC) counts on days 1, 8 and 15 every cycle, and radiological evaluations are performed every 3 cycles or earlier if clinically indicated. Pain (PPI score, Appendix B) and analgesic intake (Appendix C) are recorded on day 1 of every cycle. Correlative studies include serial CTC enumeration (repeated on day 1 cycle 2, then q 3 cycles) and collection of whole blood is performed at baseline for 20S proteasome activity. Progression of disease will be defined clinically as the first occurrence of any of the following, and PSA progression alone will not constitute progression:

1. Two distinct new lesions on bone scan consistent with bone metastases in the best judgment of the investigator and confirmed by further new lesions on a subsequent scan ≥ 6 weeks later.

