All patients will be evaluable for toxicity from the time of their first treatment with carfilzomib. CTCAE v 4.03 will be utilized to grade toxicities (Appendix). All patients included in the study will be assessed for response to treatment, even if there are major protocol treatment deviations or if they are ineligible. Each patient will be assigned one of the following categories: 1) complete response, 2) partial response, 3) stable disease, 4) progressive disease, 5) early death from malignant disease, 6) early death from toxicity, 7) early death because of other cause, or 9) unknown (not assessable, insufficient data). [Note: By arbitrary convention, category 9 usually designates the "unknown"]

status of any type of data in a clinical database.]

All of the patients who met the eligibility criteria (with the possible exception of those who received no study medication) should be included in the main analysis of the response rate. Patients in response categories 4-9 should be considered to have a treatment failure (disease progression). Thus, an incorrect treatment schedule or drug administration does not result in exclusion from the analysis of the response rate. Precise definitions for categories 4-9 will be protocol specific.

All conclusions should be based on all eligible patients. Sub-analyses may then be performed on the basis of a subset of patients, excluding those for whom major protocol deviations have been identified (e.g., early death due to other reasons, early discontinuation of treatment, major protocol violations, etc.). However, these sub-analyses will not serve as the basis for drawing conclusions concerning treatment efficacy, and the reasons for excluding patients from the analysis will be clearly reported. The 95% confidence intervals should also be provided.

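### Sections 10 and 11 give different populations for the RECIST response rate, and neither is fully usable as the denominator for measurable disease

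*Combined protocol and SAP*

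**What the plan says.** Section 2.2 lists the RECIST response rate in measurable disease as a secondary objective.

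Section 10 (Reporting and Exclusions) is inclusive. It states: "All patients included in the study will be assessed for response to treatment, even if there are major protocol treatment deviations". It then says that eligible patients, possibly excepting those never dosed, "should be included in the main analysis of the response rate. Patients in response categories 4-9 should be considered to have a treatment failure". Those categories cover progression, three kinds of early death, and an unknown category for patients who cannot be assessed. The same text rests all conclusions on the eligible patients and does not let analyses that exclude patients support efficacy conclusions. It does not mention measurable disease.

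Section 11 (Antitumor Effect) is restrictive. Only patients with measurable disease at baseline who "have received at least one cycle of therapy, and have had their disease re-evaluated will be considered evaluable for response" qualify. Its one exception reads: "Patients who exhibit objective disease progression prior to the end of cycle 1 will also be considered evaluable". Section 11 does not say that this set is subordinate to the Section 10 population, and Section 10 does not refer to Section 11.

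On timing, Section 3.1 says that "radiological evaluations are performed every 3 cycles or earlier if clinically indicated", and Section 11 gives the interval as 12 weeks. Under Section 6.3, therapy stops at clinical progression, which includes worsening pain, decline in performance status, bone events and obstruction.

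**The concern.** A patient with measurable disease who never has a second assessment is a failure under Section 10 and absent under Section 11. Conditioning on having stayed long enough to be re-imaged removes non-responders and leaves the numerator alone, so any bias in the response rate is upward. Section 10 cannot simply be adopted as it stands, because read literally it counts men with no measurable lesion, who cannot respond on this endpoint.

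At stake is the interpretation of one descriptive secondary endpoint. Section 1.1 says that measurable lesions are uncommon in this disease, so the denominator will be small and each excluded patient moves the rate visibly.

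**Working it through.** **The plan's own figure.** The protocol gives no expected response rate or sample size for response. The only design figure to reproduce is the primary test: 25 evaluable patients, reject at 6 or more, 10% against 30%. The exact binomial gives one-sided alpha 0.033 and power 0.807, in line with the stated 0.05 level and 80% power. Accrual is 25/0.9 = 27.8, hence 28. None of this depends on the response denominator.

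**The two rules side by side.**

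| Patient | Section 10 main analysis | Section 11 evaluable set |
|---|---|---|
| Measurable; dies before any re-evaluation, no objective progression in cycle 1 | In, failure | Out |
| Measurable; leaves in cycle 1 without objective progression, not re-imaged | In, failure | Out |
| Measurable; clinical progression after cycle 1, never re-imaged | In, failure | Out |
| Measurable; objective progression in cycle 1 | In, failure | In, non-responder |
| Measurable; stops for toxicity after at least one cycle, scanned off treatment | In, by scan | In, by scan |
| No measurable disease at baseline | In, cannot respond | Out |

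The first three rows are the conflict. The last row is a restriction that the endpoint itself requires, so it is not inflation.

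**Direction.** Among patients with measurable disease, let m be the number treated, x the responders and d the patients in the first three rows. Keeping them gives x/m; dropping them gives x/(m − d). The ratio is m/(m − d), which is at least 1 and equals 1 when d = 0.

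**When the first scheduled scan falls.** Three cycles of 28 days are 84 days, or 12 weeks. A patient who stops for clinical progression before then has a scan only if one is done early or after treatment.

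**Size.** The documents give no m, x or d, so all the counts below are assumptions.

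- m = 12, x = 2, d = 4: 2/12 = 16.7% (exact 95% CI about 2% to 48%) against 2/8 = 25.0% (about 3% to 65%). The ratio is 12/8 = 1.5.
- m = 14, x = 3: 3/14 = 21.4% (4.7% to 50.8%) with all kept. With d = 3, 3/11 = 27.3% (6.0% to 61.0%). With d = 4, 3/10 = 30.0% (6.7% to 65.2%). With d = 6, 3/8 = 37.5% (8.5% to 75.5%). The ratios are 1.27, 1.40 and 1.75.
- d = 0: no difference for any m and x.

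**The case against.** The best defence is that the sections do different jobs. Section 11 decides who receives a RECIST category and never mentions a response rate. Section 10 decides who is counted, and its unknown category takes in those whom Section 11 cannot classify. This reading is coherent, and Section 10's wording on the main analysis favours it. It does not settle the matter: Section 11 still limits evaluability without saying that the rate is computed on a wider set, and the wider set in Section 10 is wrong for this endpoint.

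Four stronger readings are tempting, and the documents do not support them.

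- *The rate can be chosen freely once the data are in.* Section 10 names its main analysis and does not let exclusion analyses support efficacy conclusions. What is missing is a statement that the Section 11 set is such an analysis.
- *Every early failure disappears.* Objective progression in cycle 1 is kept. Patients who stop for toxicity after at least one cycle are mostly still imaged: footnote 1 of the study calendar keeps those removed for reasons other than progression under radiographic follow-up about every 90 days until progression or new therapy. Section 11 also asks for effort to document progression after symptomatic deterioration, although this does not guarantee a scan.
- *The plan's PFS rates bound the exclusions.* With a constant hazard (an assumption), 1 − 0.30^(84/182.6) = 43% and 1 − 0.10^(84/182.6) = 65% would have a PFS event before week 12. These figures cover all patients, include radiographic progression and omit exits without progression. They do not bound the number excluded.
- *Responders over all 28 enrolled is the fair comparator.* That contrast mixes in the legitimate measurable-disease restriction. The comparison belongs within measurable disease.

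It also stands that the intervals in the examples overlap almost entirely, and that no hypothesis or threshold is attached to this endpoint.

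**Conclusion.** The inconsistency is real and worth correcting, at the level of a descriptive secondary endpoint. Using the Section 11 set as the denominator can only leave the response rate unchanged or raise it. That is certain for patients who are never re-imaged. For a patient who leaves in cycle 1 and is scanned later, it assumes no response on that scan.

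The groups mainly exposed are exits in cycle 1 without objective progression, and clinical progression without a scan. In the assumed examples the rate rises by a factor of 1.27 to 1.75, and by nothing if no patient falls in those groups. The true size cannot be derived from the documents. The conclusion on 6-month PFS does not change.

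**What to change.** State the same main denominator in Sections 10 and 11: all eligible, treated patients with measurable disease at baseline. Count categories 4-9, and any patient without a post-baseline scan, as non-response. In Section 11, label the set requiring one cycle and a re-evaluation as a sensitivity analysis only, and cross-refer the two sections. Report the number of patients who separate the two sets, with reasons, and an exact 95% interval for each rate.

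This changes wording only, needs no new data or visits, and follows the principle already in Section 10. The cost is that the reported response rate may be lower than under Section 11.

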Modest activity is considered clinically meaningful in this relatively heavily pretreated population with metastatic CRPC that has received abiraterone acetate and/or enzalutamide (prior chemotherapy and sipuleucel-T are allowed). The null hypothesis for this trial is that the primary endpoint of 6-month PFS <10% is not clinically meaningful and the alternative hypothesis is that the true clinical PFS of interest is $\geq 30\%$. Since we will follow all subjects for at least 6 months or until progression or death, we will not have censoring and 6 months PFS can be treated as a binomial random variable. With twenty five evaluable patients we will have 80% power for an exact binomial test at the one sided 0.05 significance level of the null hypothesis that the 6-month PFS rate is 10% if the actual rate is 30%. That null hypothesis will be rejected if 6 or more of the 25 subjects survive for 6 months progression free. Twenty-eight subjects will be accrued to allow for 10% inevaluable patients.

Sample Size/Accrual Rate

A total of 28 patients will be enrolled for this trial. Accrual period will be 6 to 12 months.

Analysis of Secondary Endpoints

The Kaplan-Meier method will be used to estimate PFS and OS rates over time with standard errors estimated using Greenwood's formula. Medians and their 95% confidence intervals will also be estimated. PSA response, PSA decline $\geq 30\%$ within 3 months, RECIST responses and regressions, pain response and CTC alterations will be analyzed as secondary endpoints. CTC changes will include changes from unfavorable ($\leq 5/7.5\text{ml}$) to favorable, and declines by $>30\%$. Pain response is defined as decline in present pain index ≥ 2 points and/or decrease in analgesics. Linear regression with PSA as the dependent variable and time as the dependent variable will be performed and used to estimate PSA DT. The association of baseline whole blood 20S proteasome level with PFS and other secondary endpoints will be examined using Cox regression to generate hypotheses for selecting suitable patients for further study.

Reporting and Exclusions

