Appendix B: PPI Patient Diary

Baseline	Day - 7	Day - 6	Day - 5	Day - 4	Day - 3	Day - 2	Day - 1

Complete a minimum of 7 days preceding Cycle 1, Day 1 dosing

Cycle #	Day 1	Day 2	Day 3	Day 4	Day 5	Day 6	Day 7

Cycle #	Day 8	Day 9	Day 10	Day 11	Day 12	Day 13	Day 14

Cycle #	Day 15	Day 16	Day 17	Day 18	Day 19	Day 20	Day 21

(choose only 1 score each day; do not report a range)

- | | |
|-------------------|------------------|
| 0 – no pain; | 3 – distressing |
| 1 – mild; | 4 – horrible |
| 2 – discomforting | 5 – excruciating |

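### Pain response needs no confirmation and no minimum analgesic reduction, so one Day 1 visit can make a stable man a responder in a trial with no control rate

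*Combined protocol and SAP*

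**What the plan says.** Section 11 (Pain response and progression) sets the analysis set: "Patients with a PPI score of at least 2, or need for analgesics, or both at baseline are assessed for the pain response". It then gives two routes to response. The PPI route reads "A pain response is defined as a two-point reduction in the PPI score from baseline without an increase in the analgesic use". The analgesic route reads "or as a reduction in analgesic use without an increase in the PPI score".

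Section 10 (Analysis of Secondary Endpoints) defines the same endpoint differently: "Pain response is defined as decline in present pain index ≥ 2 points and/or decrease in analgesics". Neither of Section 11's two safeguards appears there. Neither section names a visit, a duration, a repeat assessment or a minimum reduction in analgesics.

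On data collection, Section 3.1 says "Pain (PPI score, Appendix B) and analgesic intake (Appendix C) are recorded on day 1 of every cycle". For the PPI diary, Appendix B instructs "Complete a minimum of 7 days preceding Cycle 1, Day 1 dosing" and "choose only 1 score each day; do not report a range". The diary continues through Day 21 of each cycle, but no section says how daily scores become a baseline or visit value. Appendix C is a three-way tick-box (increased, decreased, same) about the previous 3 weeks, or the whole cycle if longer. It records no amount and makes no comparison with baseline.

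**The concern.** Section 1.4 lists pain responses among the supportive evidence for efficacy, and Section 2.2 makes them a secondary objective. In one arm, a man whose pain has not changed but who qualifies once by chance is counted exactly like a man who benefited, and nothing in the data separates the two. Each further cycle also gives another chance to qualify, so the chance rate rises with time on study.

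The analgesic route is the more exposed. One tick at one visit, of any size, is enough. Because the form refers to recent weeks, a man who raised his intake and then returned to his starting level would tick a decrease without being below baseline.

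The protocol asks for confirmation elsewhere. Bone-scan progression needs a later scan at least 6 weeks on, and the best-response table carries a 4-week confirmation entry on the two rows with complete response of target lesions. Pain, a more subjective measure, has no such requirement.

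**Working it through.** **The plan's own figure.** The plan gives no number for pain response. Its only design figure is for the primary test, and it reproduces. With X binomial and n = 25, P(X ≥ 6) is 0.033 at a 10% rate and 0.807 at 30%, against the stated one-sided 0.05 and 80% power. Pain response does not enter that calculation.

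**Inputs.** From the plan: one assessment per 28-day cycle, so 3 post-baseline visits at Day 1 of Cycles 2–4 and 6 at Cycles 2–7. Assumed, because the plan gives no value: a stable man ticks *Decreased* with probability q = 2% or 5% per visit, independently; daily PPI readings vary about a constant level with SD 0.4 or 0.5.

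**Analgesic route, any one visit.** P = 1 − (1 − q)^k.
- k = 3: 1 − 0.98³ = 5.9%; 1 − 0.95³ = 14.3%.
- k = 6: 1 − 0.98⁶ = 11.4%; 1 − 0.95⁶ = 26.5%.

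This is exact for the Section 10 wording. Section 11's condition that PPI has not risen lowers it. In simulation at q = 5% and SD 0.5, the 3-visit rate becomes 11.6% with single-day scores and 8.8% with 7-day means.

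**Allowing for progression.** Six visits require every man to reach Cycle 7. Assume instead exponential PFS at the plan's design rates, with assessment stopping at progression. The chance of still being assessed at visit j is r^j, where r = 0.10^(4/26) = 0.702 or r = 0.30^(4/26) = 0.831.
- Expected visits, Σ r^j for j = 1 to 6: 2.1 and 3.3.
- Chance response, Σ q(1 − q)^(j−1) r^j, for q = 2% / 5%: 4% / 10% at the null rate and 6% / 15% at the alternative.

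The 3-visit figures are therefore the realistic ones.

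**PPI route.** Simulation of stable men: true level uniform on 0–4, scores rounded and limited to 0–5, baseline PPI at least 2, and a fall of 2 or more at any visit.

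| Baseline / visit score | 3 visits, SD 0.4 / 0.5 | 6 visits, SD 0.4 / 0.5 |
|---|---|---|
| single day / single day | 3% / 8% | 5% / 13% |
| 7-day mean / single day | 0.03% / 0.3% | 0.07% / 0.6% |
| 7-day mean / 7-day mean | 0% / 0% | 0% / 0% |

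The below-1% result for a mean baseline with single-day visits depends on the SD. At SD 0.75 it is 4% over 3 visits. With 7-day means at both ends it stays at about 0.1% even at SD 1.0.

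**What confirmation does on the tick-box.** Two consecutive *Decreased* ticks over 3 visits: 2q² − q³ = 0.08% / 0.5%. But a man who cuts his dose once and stays there ticks *Decreased*, then *Remained the same*, and fails. Accepting any following answer other than *Increased* (also ticked with probability q) rescues him, but over 6 visits it leaves about 1 − (1 − q(1 − q))⁵ = 9% / 22%, against 11% / 27% unconfirmed. Confirmation therefore has to be judged against baseline use, which the form does not record.

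**The case against.** The strongest objection concerns the PPI route. A reader might infer that men are selected on one high, noisy reading and then regress. The documents do not establish this, because Appendix B collects at least 7 daily scores before treatment and averaging them nearly removes the effect. What stands is that no rule says the scores are averaged, and Section 3.1 describes a Day 1 recording, so single-day use is permitted.

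Second, the rates are assumed. The plan gives neither PPI variability nor a tick rate for stable men, so no false-response rate can be read from it. That is correct. The missing confirmation rule is a fact of the text; its size is not.

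Third, that one visit suffices is inferred from silence, and the comparison with tumour response is limited: as the table reads, the partial-response row for target lesions carries no confirmation entry. Both points are fair. The silence still leaves the analyst free to count a single visit.

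Fourth, the routes are not open to everyone. A man with baseline PPI 0 or 1 cannot fall 2 points, and a man on no analgesics cannot reduce them.

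Finally, pain response is one of several secondary endpoints with no test or threshold. That limits the importance of the point but does not remove it.

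**Conclusion.** The concern holds for the missing confirmation, the unquantified analgesic route and the two differing definitions. Under the assumed 2% or 5% tick rates, the analgesic route alone makes 6% or 14% of stable analgesic users responders over 3 visits. In an assumed 15 such men that is 15 × 0.059 = 0.9 or 15 × 0.143 = 2.1 false responders. The 6-visit figures of 11% and 27% are upper bounds. The PPI route matters only if single-day scores are used.

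A reader might go further and conclude that the efficacy conclusion is compromised. The documents do not support that: the primary test, its decision rule and the sample size do not use pain response. What is weakened is the reading of an uncontrolled pain-response rate as supportive evidence. This should be corrected, but it does not threaten the design.

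**What to change.** - Use one definition in Sections 10 and 11: Section 11's guarded wording.
- Take baseline PPI as the mean of the 7 pre-treatment diary scores, and visit PPI from the diary days nearest Day 1. Name those days, since the diary has no rows for Days 22–28.
- Require the criterion, judged against baseline, to hold at two consecutive Day 1 assessments.
- For the analgesic route, judge reduction against baseline use from the concomitant-medication record, which Section 7 starts 14 days before Day 1 and in which every change must be entered. Do not use two consecutive *Decreased* ticks, so that a single sustained reduction still counts.
- Count men without a confirming assessment as non-responders, and report single-visit responses descriptively.

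The cost is SAP and protocol wording plus some coding of medication records, which must hold enough detail on amounts to show a reduction. No visits are added. The stated pain-response rate will be lower, and men who leave after one good visit will not count.
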